**Table 3-4: Planned Dose Escalation Levels**

Level	N	TTI-621 dose (mg/kg)		
		Week 1b	Week 2	Week 3
0	3 (+ 3)	0.2	0.5	0.5
1 a	3 (+ 3)	0.5	0.5	0.5
2	3 (+ 3)	0.7	0.7	0.7
3	3 (+ 3)	1.0	1.0	1.0
4	3 (+ 3)	1.4	1.4	1.4

a Level 1 = starting dose

b If de-escalation to level 0 is required, all subsequent cohorts will start with a priming dose of 0.2 mg/kg at week 1 followed by the respective dose level escalation increments (0.7, 1.0, 1.4 mg/kg) at week 2 or subsequent weeks, as applicable, based on SRC decision.

In the starting dose level (0.5 mg/kg), the first 3 patients will be treated sequentially to allow close monitoring of toxicity and timely dose adjustment if needed. The third patient will not start the study treatment until the first and second patient, respectively, have completed the initial two weeks of study treatment and had no observation of TEAEs meeting DLT criteria. If the first or second patient experiences a DLT event within the first two weeks of treatment, de-escalation to Level 0, a priming dosing regimen, will be considered per SRC discussion and decision. A priming regimen refers to a dosing regimen that involves a lower priming dose used during the initial week(s) of treatment followed by further dose escalation to a higher and stable dose for continued use throughout the course of the study. At Level 0, patients will be dosed at 0.2 mg/kg for the first week and then receive a stable dose of 0.5 mg/kg for the remainder of the study.

If Level 0 is determined to be tolerable per 3+3 schema, further escalation of doses beyond 0.5 mg/kg in Week 2 and beyond will be considered, as part of the priming dosing regimen. The same dose escalation increment (to 0.7, 1, and 1.4 mg/kg) may be followed after the initial week of exposure to 0.2 mg/kg.

The MTD is defined as the dose level immediately below the lowest dose that at which 2 or more of either 3 or 6 patients experienced a DLT during the 3-week DLT period. At least 6 patients must be treated at the putative MTD, with no more than 1 incidence of DLT. AEs that occur after the 3-week DLT period or cumulative toxicities will be considered in the final designation of MTD.

If MTD is not reached after completion of all planned dose escalation levels, a decision will be made in consultation with the SRC (see [Section 3.4](#)), to either continue further escalation at a maximal 50% escalation increment, or dose escalation will be halted. A maximum assessed dose (MAD) could be used in lieu of the MTD. The SRC will review the totality of the safety, tolerability, PK, PD, and preliminary efficacy data (if available) before making this decision.

In addition to MTD/MAD determination, SRC will review the totality of cumulative toxicity and tolerability data in balance against the PK, PD and preliminary efficacy data. If a biologically active dose appears to be lower than MTD/MAD or if the MTD/MAD results in dose modification due to tolerability that limits continued dose exposure and in turn compromise the potential efficacy gain, a recommended phase 2 dose of TTI-621 lower than MTD/MAD can be determined for future single agent studies. Minimally 6 patients will need to be evaluated at the recommended phase 2 dose before formal designation.

After MTD/MAD or recommended phase 2 dose (if different from MTD/MAD) is determined, an additional 6 patients will be enrolled and treated at this dose level to form a safety expansion cohort of a total of 12 patients (including the 6 patients treated at the designated phase 2 dose before the dose selection). Preliminary efficacy will also evaluated in this cohort of patients.

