## 1.7 Anticipated or Possible Risks in Human Subjects

### *Summary of Dose-Escalation Safety Data*

Data from the first 18 subjects enrolled in the dose-escalation phase of the study show that TTI-621 has been reasonably well tolerated. Transient, dose-dependent decreases in platelets without clinical sequelae occurred in the hours following infusion in the majority of subjects exposed to TTI-621. Thrombocytopenia was relatively brief with recovery to baseline platelet counts by the next weekly dose and appeared attenuated with weekly TTI-621 exposure. Other Grade 3/4 cytopenias (monocytes, neutrophils, and lymphocytes) were also frequently observed; all were transient and resolved without sequelae.

The majority of subjects experienced mild to moderate infusion-related reactions (IRRs) that typically occurred after the first TTI-621 infusion only. IRRs were reported across all dose cohorts with no obvious dose relationship and occurred despite premedication with an antihistamine and acetaminophen.

Three subjects experienced reversible Grade 3 hypophosphatemia in the days following their first infusion of TTI-621. Hypophosphatemia in 1 of the 3 subjects was considered related to TTI-621 and was therefore reported as a DLT. The event rapidly resolved without intervention. Hypophosphatemia was considered unrelated to TTI-621 in the other 2 subjects and their phosphate levels were corrected by oral phosphate.

No subjects in either the 0.05 mg/kg/week or 0.1 mg/kg/week dose groups experienced dose-limiting toxicity (DLT). However DLTs were reported for 2 of 5 subjects treated at the 0.3 mg/kg/week dose: 1 subject with Grade 4 thrombocytopenia and 1 subject with Grade 4 thrombocytopenia and Grade 3 elevated alanine aminotransferase/aspartate aminotransferase (ALT/AST). Upon review of cumulative adverse events (AEs) and laboratory values, the Safety Review Committee (SRC) recommended proceeding with

enrollment at an intermediate dose level of 0.2 mg/kg TTI-621 (Cohort 2a), and to dose reduce all subjects participating in the 0.3 mg/kg cohort to the 0.2 mg/kg dose level (one subject was dose reduced to the 0.1 mg/kg dose level).

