#### 1.8.4 Rationale for Phase 1b Dose Optimization (Part 4)

[figure not shown]
During phase 1a dose escalation (Part 1), weekly infusion of TTI-621 at 0.2 mg/kg was determined to be the MTD per 3+3 dose escalation as planned. Two Grade 4 events of asymptomatic thrombocytopenia were observed in 2/3 patients dosed at 0.3 mg/kg. Per the DLT criteria in phase 1a, these two events were determined to be a DLT which led to the conclusion that 0.3 mg/kg exceeded MTD. The majority of the patients treated during Phase 1b dose expansion Part 2 received weekly infusions of 0.2 mg/kg TTI-621. Based on a safety analysis of 179 patients by a data cut of 01 October, 2018, the majority of patients (143; 80%) had abnormal platelet counts reported at 1 or more timepoints post dose, with 49 subjects (27%) experiencing Grade 4 decreases, including both TTI-621-induced events, and events resulting from the underlying hematologic malignancies. As shown in [Figure 1-3](#), platelet counts decreased acutely on dosing days but generally recovered within the week prior to the next dose. Overall, pre-infusion platelet counts remained stable over the course of the study. Additionally, due to the transient and reversible nature of the thrombocytopenia, no apparent increase in the incidence of bleeding has been observed on study. A total of 24/179 subjects (13%) experienced a treatment-emergent bleeding event (see [Table 1-1](#)).

Overall, 20/179 subjects (11%) experienced Grade 1 or 2 events and 4 subjects (2%) had Grade 3 bleeding events. Grade 3 hemorrhage events were considered treatment-related for 3 subjects (2%). No Grade 4 hemorrhage events were reported. Therefore, based on the expanded safety data in which the clinical significance of thrombocytopenia is now better understood, the original DLT criteria have been reassessed and revised. The major revision of the DLT criteria in comparison to those in Phase 1a is that Grade 4 thrombocytopenia is no longer a DLT unless it lasts for more than 72 hours. With this revision, the two original DLT events of Grade 4 thrombocytopenia would no longer be qualified as DLTs, so 0.3 mg/kg should not have exceeded MTD. Therefore, further dose escalation per revised DLT criteria to re-define MTD or recommended Phase 2 dose is warranted. This effort is further justified by the safety data collected thus far from selected patients who dose intensified on

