## 3.2 Phase 1a Escalation (Completed)

### 3.2.1 Dose Advancement and MTD Determination

A minimum of 3 subjects will be treated in each dose cohort in a conventional 3 + 3 design ([Table 3-1](#)) starting at Cohort 1. Given the potential risk for cytokine release syndrome, the first subject in each dosing cohort will be treated and observed for 72 hours before the next subject can receive their first infusion of TTI-621. Cohort 0 represents a contingency de-escalation dose level in the event that tolerance issues are encountered in Cohort 1. Treatment for an individual subject is described in [Section 6.3](#).

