### 3.3.2 Phase 1b Dose Optimization Part 4 (to be enrolled as of Amendment 9)

A minimum of 3 patients will be treated in each cohort sequentially in a 3 + 3 design. The planned dose escalation levels are shown in [Table 3-4](#). Patients will receive once weekly dosing of TTI-621 at the dose levels in their assigned cohort regimen (Week 1 given on Day 1, Week 2 given on Day 8, and Week 3 given on Day 15). The DLT observation period is 21 days. Patients will be considered evaluable for DLT if they receive all 3 weekly doses within the DLT evaluation period or if they experience an AE meeting DLT criteria during that time. If a patient experiences a non-DLT event that requires a dose to be held per dose modification guideline ([Section 6.5](#)), the DLT evaluation period can be extended to 28 days. If a DLT occurs in 1 of 3 patients within a cohort, 3 additional patients will be treated at that cohort regimen. In the absence of DLT, enrollment will proceed sequentially through the planned dose levels.

Alternative dose escalation including evaluation of intermediate doses, expansion of an existing dose level, evaluation of alternative regimens/schedules including a dose ramp-up design following different dose intensification increments and schedule, and modification of dosing frequency and/or IV infusion rate are all permissible if supported by the evolving data and a SRC decision. All patients in each cohort must have completed the 21-day DLT period before the next cohort begins treatment. The MTD of TTI-621 will be the dose below the one in which  $\geq 2$  DLTs are observed among 6 treated patients.

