### Phase 1b Dose Optimization Phase (Part 4)

Once a subject is deemed eligible, Part 3 of the Registration/Enrollment Form will be completed and sent to the Sponsor or designee, at which time the TTI-621 dose level will be assigned. Additional instructions may be found in the separate Study Manual.

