### 6.4.1 TTI-621 Monotherapy

#### Phase 1b – Part 2 and Part 3

Subjects enrolled in these cohorts will receive a starting dose of 0.2 mg/kg/week TTI-621. For Part 3, intrasubject TTI-621 dose-intensification is required for newly enrolled subjects. All subjects will receive a dose ramp-up regimen which includes initial two-weeks of 0.2 mg/kg treatment followed by intrasubject dose intensification at an increment of 0.1 mg/kg per week up to 0.5 mg/kg within 5-8 weeks. Details regarding when dose intensification should be delayed or stopped due to AEs are provided in [Section 6.5.3](#).

#### Phase 1b Dose Optimization - Part 4

Subjects in the phase 1b dose optimization phase (Part 4) will undergo dose escalation of TTI-621, starting with Level 1 (dose of 0.5 mg/kg) per dose escalation plan (See [Table 3-4](#), [Section 3.3.2](#)) given once weekly. Following a 3+3 escalation design and using a revised DLT criteria, enrollment will continue through Level 2 (starting dose of 0.7 mg/kg), Level 3 (starting dose of 1.0 mg/kg) and Level 4 (starting dose of 1.4 mg/kg) respectively. In the starting dose cohort (0.5 mg/kg), the first 3 patients will be treated sequentially to allow close monitoring of toxicity and timely dose adjustment if needed. The second and third patient will not start the study treatment until the first and second patient, respectively, have completed the initial 2 weeks of study treatment and had no observation of TEAEs meeting DLT criteria. If a DLT is noted in Level 1, there may be de-escalation to Cohort 0 (priming dose of 0.2 mg/kg at week 1 followed by 0.5 mg/kg at subsequent doses) with progression through Levels 2, 3 and 4 using the dose priming approach of 0.2 mg/kg at week 1 followed by the respective level dose regimens at subsequent weeks.

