### **1.2.5 Phase 1b Dose Optimization – Part 4**

In the dose optimization phase, Part 4, the safety and tolerability of TTI-621 at higher dose levels beyond the initially recommended Phase 1b dose of 0.2 mg/kg (as determined during Phase 1a dose escalation) and the highest dose of TTI-621 evaluated (0.5 mg/kg) during Phase 1b dose expansion following dose intensification permissible per protocol, will be evaluated. This Phase 1b dose optimization phase will aim at re-defining MTD following 3+3 dose escalation schema and a revised DLT criteria based on the totality of safety data collected thus far from Phase 1a and 1b dose expansion phase of the study. In Phase 1b dose optimization of the study (Part 4), further dose escalation of TTI-621 will be pursued in subjects with relapsed and/or refractory CTCL following a 3+3 escalation design and using a revised DLT criteria. Dose optimization will proceed following review of the data obtained from the Phase 1b Part 3, stage 1 cohorts of CTCL and PTCL subjects. Alternative dosing schedules, intermediate doses, and other optimization options may be considered by the SRC following review of available data.

Part 4 Q2W is an expansion to Part 4 Cohort 5 (P4-5). Dosing is done at the 2.0 mg/kg dose level and explores a TTI-621 biweekly (every other week) dosing schedule.

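### The protocol gives two different stagger rules for the first three patients at unprimed 0.5 mg/kg in Part 4, and one of them sets no wait for the second patient

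*Protocol*

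**What the plan says.** The stagger for the Part 4 starting cohort (Level 1, 0.5 mg/kg in each of Weeks 1 to 3 in Table 3-4) is stated four times. All four statements say that the first three patients are treated one after another so that toxicity can be watched. They then divide.

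- Protocol section 3.3.2 (text below Table 3-4) and the Synopsis, study design: "The third patient will not start the study treatment until the first and second patient, respectively" have had two weeks of treatment without an event meeting the DLT criteria.
- Protocol section 6.4.1 (Part 4) and the Synopsis, treatment procedures: "The second and third patient will not start the study treatment until the first and second patient, respectively" have met the same condition.

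Other Part 4 text bears on timing without setting an interval between patients. Section 3.3.2 gives the dosing days within a patient: "Week 1 given on Day 1, Week 2 given on Day 8, and Week 3 given on Day 15". Section 5 has the registration form sent to the sponsor or its designee, "at which time the TTI-621 dose level will be assigned". Section 3.4 has the Safety Review Committee (SRC) meet once all 3 or 6 subjects of a cohort can be assessed for DLT. The SAP does not state the stagger rule.

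**The concern.** The two wordings agree on patient 3 and differ on patient 2. Under section 6.4.1, patient 2 waits until patient 1 has two DLT-free weeks. Under section 3.3.2, patient 2 comes after patient 1, but with no minimum gap and no DLT-free condition.

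This is an operative safety rule for the first use of 0.5 mg/kg without a lower lead-in dose. The 0.5 mg/kg experience described in section 1.8.4 came from patients who began at 0.2 mg/kg and were stepped up, with platelet assessments at 0.5 mg/kg taken in Weeks 5 to 30. Section 1.7 reports that the platelet drop appeared to lessen with weekly exposure and that infusion reactions typically followed the first infusion only, so that experience may not carry over to a first dose. The highest unprimed dose with escalation results in the protocol is 0.3 mg/kg; Level 1 is 67% above it (0.5/0.3 = 1.67). Section 3.3.2 is the main design section, and section 6.4.1 itself sends the reader there for the escalation plan.

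**Working it through.** **Does any other text supply a wait for patient 2?**

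- *Sequentially* appears in all four statements, yet section 6.4.1 and the Synopsis treatment text still add the hold on patient 2. Section 3.3.2 also uses the word for every cohort, where no two-week stagger applies. It sets an order, not an interval.
- *Respectively* in section 3.3.2 pairs two earlier patients with only one held patient. It makes sense only with two held patients, so the words naming the second patient were probably dropped.
- The one explicit interval after a first patient is in section 3.2.1: "the first subject in each dosing cohort will be treated and observed for 72 hours before the next subject can receive their first infusion". That section governs Phase 1a.
- Under section 3.4, no scheduled SRC review falls between patients 1 and 2.

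No other text supplies it.

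**How much exposure is at stake?** Let g be the number of days from patient 1's start to patient 2's start, with g ≥ 1 because the patients are sequential. Patient 2's first two doses (own Days 1 and 8) fall on patient 1's Days 1 + g and 8 + g. Patient 1 completes two weeks at the end of Day 14.

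- Both doses fall within that time if 8 + g ≤ 14, so g ≤ 6. For g = 1 they fall on Days 2 and 9; for g = 6, on Days 7 and 14.
- One dose does if 7 ≤ g ≤ 13.
- None does if g ≥ 14, which is what section 6.4.1 requires.

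These are nominal days. The opening of section 7 allows ±2 days from Week 2 on, so the second dose can fall anywhere from Day 6 + g to Day 10 + g. The change from two doses to one then moves from g = 6 to somewhere between g = 4 and g = 8. The retreatment criteria in section 6.5.2 could also delay the second dose.

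**Timing of patient 3.** The earliest start, in days after patient 1's start, is 14 + g under the literal section 3.3.2 wording and 14 + 14 = 28 under section 6.4.1. The difference is 14 − g.

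| g (days) | Section 3.3.2, literal | Section 6.4.1 | Difference (days) |
|---|---|---|---|
| 1 | 15 | 28 | 13 |
| 3 | 17 | 28 | 11 |
| 7 | 21 | 28 | 7 |

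**Chance that it matters.** Let p be the probability of a DLT within two weeks. Patient 2 can be dosed without waiting out a DLT in patient 1 only if patient 1 has one, so the chance is at most p under the literal section 3.3.2 wording and 0 under section 6.4.1. The documents do not give p. Assuming 5%, 10% or 20%, the bound is 5%, 10% or 20%.

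The top of that range has a rough anchor. Section 1.7 reports DLTs in 2 of 5 subjects at 0.3 mg/kg: one with Grade 4 thrombocytopenia alone, and one with Grade 4 thrombocytopenia plus Grade 3 ALT/AST elevation. Section 1.8.4 says: "With this revision, the two original DLT events of Grade 4 thrombocytopenia would no longer be qualified as DLTs". At most the ALT/AST subject then remains, 1/5 = 20% (exact 95% CI 0.5% to 71.6%). That count covers three weeks at a lower dose, and section 1.8.4 gives the denominator as 3 rather than 5. It illustrates the range and does not estimate p.

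**The case against.** The strongest reply is that this is a slip of the pen and not two competing rules. Section 3.3.2 does not say that patient 2 may start at once; it is silent, section 6.4.1 fills the gap, and a site that follows section 6.4.1 breaches none of the four statements. Starting patients 1 and 2 almost together would also defeat the stated purpose of close monitoring. Safeguards exist: the sponsor or designee assigns the dose level for each patient, a DLT in patient 1 or 2 within two weeks prompts SRC consideration of the primed Level 0, and Week 1 blood counts are frequent (section 7.3). The probability bound only returns the value assumed for p. And the cohort has probably been dosed already: SAP version 2.0 (02NOV2022), section 1.2.5, describes a Part 4 Cohort 5 at 2.0 mg/kg, above the top planned level of 1.4 mg/kg.

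Much of this stands. The intended rule is not in serious doubt, the safeguards make the worst case less likely, and the probability figures should carry little weight. But none of the safeguards states an interval for patient 2, and a reader of section 3.3.2 alone has to infer words that are not there. That one wording satisfies all four statements shows which one to keep; it does not make them agree.

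**Conclusion.** The inconsistency is real and should be fixed. Two of the four statements of a first-dose safety rule omit the hold on the second patient, and nothing else in the protocol or SAP provides it. Taken literally, they allow two patients instead of one to be exposed to unprimed 0.5 mg/kg before the first two-week DLT check, with patient 2 receiving up to two doses in that time on nominal dosing days. The reach is narrow: the first three patients of one cohort, with no effect on sample size, error rates, the MTD rule or any analysis. The conclusion rests on the text alone. The dose counts assume the nominal Day 1 and Day 8 schedule, and the 5% to 20% DLT range is an assumption.

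**What to change.** In section 3.3.2 and in the Synopsis design text, replace the sentence that holds only the third patient with the one already in section 6.4.1, beginning "The second and third patient will not start the study treatment until the first and second patient, respectively", so that all four places carry one rule. This is one sentence in two places. It adds no delay to the schedule that section 6.4.1 already requires. Against the literal section 3.3.2 wording, patient 3 would start up to 13 days later, in this one cohort only.

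If the 0.5 mg/kg cohort has already been treated, as the SAP suggests, the edit protects nobody in this trial. The useful step is then one line in the study report stating which rule was applied to patient 2.

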### **3.3.3 Definition of Dose-limiting Criteria for Phase 1b Part 4 (Amendment 9)**

Dose-limiting toxicity is defined as any of the following TAEs that occur during the 21-day DLT treatment/observation period (including the pre-dose tests on Day 22/Week 4 Day 1) and that are considered at least possibly related to study treatment by the investigator. Note that any AEs for which the relationship to study treatment cannot be ruled out should be considered possibly related:

#### **Hematologic toxicity**

- Grade 4 thrombocytopenia ( $<25 \times 10^9/L$ ) lasting  $>72$  hours or a platelet count  $\leq 10 \times 10^9/L$  at any time

- $\geq$  Grade 3 thrombocytopenia with bleeding (except epistaxis or gingival bleeding that is less than 24 hours in duration and does not require medical intervention, or normal menses) or requiring platelet transfusions
- Grade 4 anemia, unexplained by underlying disease
- Grade 4 neutropenia lasting  $>72$  hours
- Grade 3 febrile neutropenia lasting  $>72$  hours
- Grade 4 febrile neutropenia

#### Non-hematologic toxicity

- Grade 3 or higher non-hematologic toxicity with the following exceptions:
  - Grade 3 nausea and/or vomiting lasting  $<72$  hours with standard supportive care
  - Transient Grade 3 fatigue lasting  $\leq 72$  hours
  - Transient asymptomatic Grade 3 laboratory abnormalities considered not clinically significant following agreement between investigators and the sponsor's medical monitor and that last  $<72$  hours with standard supportive care
- Other  $\geq$  Grade 2 TTI-621-related non-hematologic toxicities that, in the opinion of the investigator, require a dose reduction or discontinuation of TTI-621

